#### Relationship statements

University Hospitals Bristol and Weston Foundation NHS Foundation Trust are the Sponsoring organisation and will delegate some Sponsor responsibilities to the CTU, University of Warwick and the Chief Investigator; they will be legally responsible for the UK arm of the trial. The CTU based in Warwick will have overall management responsibility for the trial from a CTU perspective, and will be responsible for co-ordination of all centres.

University of Warwick are Co-Sponsor, they will collaborate with the CTU and will act as sole sponsor for non-UK centres i.e. they are legally responsible for the non-UK arm of the trial.

#### **TRIAL SUMMARY**

Trial Title	Randomised trial of the clinical and cost effectiveness of					
	during in-hospital cardiac arrest (AIRWAYS-3)					
Internal ref. number (or short title)	AIRWAYS-3					
Trial Design	A multi-centre, open-label, pragmatic, individually randomised, parallel group, superiority trial and economic evaluation to determine the clinical and cost effectiveness of a supraglottic airway (SGA) versus tracheal intubation (TI) during in-hospital cardiac arrest (IHCA). The trial will include an internal pilot to confirm feasibility					
Trial Participants	Adult (known or believed to be age >=18) hospital inpatients will be eligible for randomisation if they receive resuscitation following IHCA that requires a 2222 call and advanced airway management					
Planned sample size	4190 participants from centres throughout the UK and internationally					
Treatment Duration	Until return of spontaneous circulation (ROSC) for >20 minutes or resuscitation efforts cease, after which the airway will be managed by the attending team as they feel appropriate					
Follow-up Duration	6-months post IHCA					
Planned Trial Period	1 st January 2022 – 31 st December 2026					
Trial Objectives	
 
(1) Conduct an internal pilot study to confirm the feasibility of the large-scale multi-centre trial
 
(2) Determine the clinical effectiveness of SGA management, for adults with in-hospital cardiac arrest, in terms of survival with a favourable functional outcome and health-related quality of life.
 
(3) Estimate, in an integrated economic evaluation, the cost-effectiveness of SGA compared with TI
 
					
Primary Outcome Measure	Functional status at hospital discharge (or 30 days post- randomisation whichever is shorter) as measured by the modified Rankin Scale (mRS)					
Secondary Outcome Measures	
 
Initial ventilation success
 
Regurgitation/aspiration during resuscitation
 
Return of Spontaneous circulation (ROSC) >20 minutes
 
					

	
 
ICU and hospital length of stay
 
					
	Health-related quality of life at discharge, 3 and					
	6 months)					
	• Survival to hospital discharge, 3 months and 6					
	months					
	
 
Functional status (mRS) at 3 and 6 months
 
					
Economic outcomes	Additional unscheduled care and re-admissions					
	(to 6 months)					
	
 
In-hospital stay utilisation and cost
 
					
Safety outcomes	Adverse event/serious adverse events					

# LIST OF ABBREVIATIONS/GLOSSARY

Abbreviation	Explanation
AE	Adverse Event
CAG	Confidentiality Advisory Group
CI	Chief Investigator
CONSORT	Consolidated Standards of Reporting Trials
CRF	Case Report Form
CTU	Clinical Trials Unit
DMC	Data Monitoring Committee
GCP	Good Clinical Practice
GDPR	General Data Protection Regulation
HES	Hospital Episode Statistics
ICF	Informed Consent Form
ICNARC	Intensive Care National Audit & Research Centre
IHCA	In Hospital Cardiac Arrest
IRAS	Integrated Research Application System
ISRCTN	International Standard Randomised Controlled Trial Number
MRC	Medical Research Council
mRS	Modified Rankin Scale
NCAA	National Cardiac Arrest Audit
PI	Principal Investigator
PPI	Patient & Public Involvement
PWA	Progressive Web App
QoL	Quality of Life
RCT	Randomised Controlled Trial
REC	Research Ethics Committee
R&D	Research and Development
ROSC	Return of Spontaneous Circulation
SAE	Serious Adverse Event
SGA	Supraglottic Airway
SOP	Standard Operating Procedure
ТІ	Tracheal Intubation
TSC	Trial Steering Committee
WCTU	Warwick Clinical Trials Unit

# 1. BACKGROUND

# **1.1** Epidemiology and burden of the condition

In hospital cardiac arrest (IHCA) occurs when the heart stops beating suddenly and is an extreme medical emergency. The estimated incidence of IHCA in the UK, as captured by the National Cardiac Arrest Audit (NCAA), is 1 patient per 1000 hospital admissions, although the true figure is likely to be higher as the NCAA includes only those patients who are attended by a resuscitation team in response to a 2222 call (13). IHCA has significant mortality and morbidity. Current survival to hospital discharge following resuscitation for IHCA in the United Kingdom (UK) is approximately 24% (1), however additional UK data collected by members of our research team suggest that survival is closer to 10% in those patients who require advanced airway management (the insertion of a tracheal tube or a supraglottic airway device to ventilate the lungs with supplemental oxygen).

During a cardiac arrest, the brain is exposed to critically low oxygen levels, which may result in death or long-term cognitive deficits. Survivors of cardiac arrest who are discharged from hospital commonly describe cognitive impairment. The frequency of this impairment varies because recommended outcome measures report a crude assessment of general neurological function, which often appears good in the majority of cases (2,3). However, in studies using more detailed neuropsychological instruments, cognitive impairment is present in 30-50% of survivors (4,5), and associated with a lower quality of life and increased caregiver strain (5,6).

Following IHCA immediate and effective cardiopulmonary resuscitation (CPR) is central to achieving a good patient outcome. However, chest compressions alone do not provide adequate lung ventilation during prolonged CPR. Effective airway management is essential to ventilate the lungs with supplemental oxygen while minimising the risk of gastric regurgitation and pulmonary aspiration.

Research on interventions to improve survival, and the quality of survival, remains highly relevant and important to the needs of the NHS, both now and in the future. The societal impact of cardiac arrest is substantial and evidenced by both the years of productive life lost due to death and disability and the economic burden of caring for cardiac arrest patients who are resuscitated successfully but are left with significant functional impairment (17).

# 1.2 Existing knowledge

There are very few studies or data sources available to measure IHCA incidence and outcomes, particularly when compared with out of hospital cardiac arrest (OHCA). Observational studies of resuscitation outcomes also tend to be confounded by resuscitation time bias: patients with the best outcomes will be resuscitated (achieve a return of spontaneous circulation) quickly, and before advanced airway management is needed. Therefore, patients who do not require advanced airway management tend to have better outcomes (12,18).

While tracheal intubation (TI) has been considered the definitive technique for advanced airway management during IHCA (7), recent RCTs in out-of-hospital cardiac arrest (OHCA) suggest that there may be advantages to using supraglottic airway (SGA) devices instead of TI as the preferred form of advanced airway management during cardiac arrest (20,21). SGAs are generally quicker and easier to insert (22) and may reduce the frequency and duration of pauses in chest compressions (23).

Members of the AIRWAYS-3 trial team have recently completed the NIHR-funded AIRWAYS-2 trial of tracheal intubation versus the i-gel supraglottic airway device in OHCA (HTA Project: 12/167/102). This did not detect a significant difference in functional outcome (including mortality) between the two advanced airway management techniques at 30 days, 3 months and 6 months after OHCA

(21,24). Since then, updated international resuscitation guidelines support the use of supraglottic airways (SGAs) in settings where intubation success rates are lower (11). Changes have followed in systems where paramedics manage the airway during out of hospital cardiac arrest (OHCA), but not where doctors are the airway provider including some European pre-hospital systems and all inhospital cardiac arrests (25,26). The outstanding clinical question is therefore whether SGAs are superior to tracheal intubation in situations where intubation success rates are assumed to be high.(11) Our national survey and a recent international study both demonstrate substantial practice variation and equipoise in IHCA (9,27). OHCA is fundamentally different to IHCA in terms of the causes of cardiac arrest, prognosis and time to advanced airway intervention (28,29). There are also substantial differences between IHCA and OHCA patients; arrests of cardiac cause, and shockable rhythms, are more frequent in OHCA than IHCA patients, while IHCA is much more commonly due to hypoxaemia making the choice of airway management particularly relevant in the IHCA patient group.(13,28,30) International consensus guidelines and clinical practice make it clear that the results from AIRWAYS-2 cannot be extrapolated to IHCA, and that uncertainty persists regarding the best advanced airway management technique during IHCA (11).

A recent (2019) systematic review of advanced airway management during cardiac arrest was conducted to inform the International Liaison Committee of Resuscitation (ILCOR) consensus on CPR science and treatment recommendations, and a member of our team ([name]) authored the review and chaired the process (11). A repeat of these searches (up to 05 January 2021), and a search of the WHO International Clinical Trials Registry Platform for any relevant studies that are planned or in progress identified one further published study (31), and that no relevant trials were being planned or underway. As is the case for cardiac arrest trials in general (12), the ILCOR review found that studies in OHCA far outnumbered studies in IHCA. No controlled trials in the IHCA setting were identified. Only 9 of the 78 observational studies exclusively included IHCA patients and only 3 of these met the review's inclusion criteria. Following its systematic review, ILCOR identified the optimal airway management strategy for IHCA as a significant knowledge gap (11), with additional high-quality studies of airway management in IHCA required as an urgent priority (12).

To understand current practice, and whether there is equipoise in the UK, an online survey and telephone interviews with trainee doctors in anaesthesia and intensive care, identified by the UK Research and Audit Federation of Trainees, was completed to inform this proposal (9). The aims of this research were to: examine current airway management practice during adult IHCA; explore participants' attitudes to potential participation in a randomised trial of airway management during IHCA; explore the feasibility of proposed aspects of trial design; identify potential barriers and facilitators. Completed surveys were received from 128 hospital sites (76% response rate). The majority (96%) of respondents reported immediate access to both TI and SGAs. SGAs were used 'very frequently' or 'frequently' during in-hospital cardiac arrest by 79% of respondents, whilst TI was used 'very frequently' or 'frequently' by 69%. Attitudes towards a randomised trial of airway management strategies during IHCA were highly positive with 80% 'likely' or 'very likely' to participate. As TI and SGA devices are both readily available and used with similar frequency, participants felt there was equipoise in relation to this research question. Randomisation would not cause substantial divergence from usual practice and would therefore be ethically acceptable. These findings have been used to inform and improve our trial design.

#### 1.3 Hypothesis

During IHCA, airway management with a SGA is clinically superior and cost-effective when compared with TI.

# 1.4 Need for a trial

The International Liaison Committee on Resuscitation has highlighted the urgent need for research on airway management during IHCA to improve the quality of care and consequent clinical outcomes.(19) Tracheal intubation skills are limited to relatively few individuals, whereas bag-mask ventilation and the insertion of a SGA can be completed successfully by a wider range of healthcare staff. This has important implications for the composition and function of in-hospital cardiac arrest teams, with an opportunity for improved efficiency.

### **1.5** Ethical considerations

The trial will be conducted in full conformance with the principles of the Declaration of Helsinki and Good Clinical Practice (GCP) guidelines. It will also comply with all applicable UK legislation including the Mental Capacity Act 2005 and the National Health Service Act 2006 as well as Warwick Standard Operating Procedures (SOPs). All data will be stored securely and held in accordance with the UK General Data Protection Regulation (UK GDPR).

This trial raises several important ethical issues, which have been considered carefully in the development of this protocol, drawing on the relevant legal and regulatory frameworks and previous experience from successful trials in cardiac arrest, involvement in the Health Research Authority Forum on Consent in Emergency Research, and detailed consultation with patients and the public.

The immediately incapacitating nature of cardiac arrest (sudden loss of consciousness) means that it will not be possible to obtain prospective informed consent from participants. Because of the need for immediate treatment, it will also not be possible to obtain an opinion from a personal or professional consultee. Using the provisions within the Mental Capacity Act 2005 Section 32, approval from a Research Ethics Committee to enrol patients without prior consent will be sought. If the patient survives the initial event, and once they have recovered sufficiently (usually once they are recovering on a general hospital ward), a member of the hospital research team will approach the patient (or if they lack capacity, a consultee) whilst they are still in hospital. They will explain the study and seek consent to continue in the trial. However, differential agreement to participate in follow-up arising from early differences in mortality could introduce bias. To avoid this, and ensure 100% data ascertainment of the primary outcome (modified Rankin Scale Score at hospital discharge, or 30 days if the patient remains in hospital at this time), the primary outcome will be collected for all enrolled patients from routinely available data collected locally and by the National Cardiac Arrest Audit with the prior permission of the Health Research Authority Confidentiality Advisory Group (CAG).

# 1.6 CONSORT

The trial will be reported in line with the CONSORT (*Con*solidated Standards of Reporting Trials) statement (55).

# 2. TRIAL DESIGN

#### 2.1 Trial summary and flow diagram

This is a multi-centre, open-label, pragmatic, individually randomised, parallel group, superiority trial and economic evaluation to determine the clinical and cost effectiveness of SGA versus TI during IHCA. The trial will be conducted in the acute setting in NHS hospitals throughout England and Wales and some international hospitals outside of the UK.

An internal pilot study will confirm the feasibility of the trial. An integrated economic evaluation will assess the cost-effectiveness of SGA compared with TI.

The primary outcome is the Modified Rankin Scale (mRS) score assessed at hospital discharge or 30 days following IHCA, whichever occurs sooner.

#### Figure 1 Trial flow diagram

# Randomised trial of the clinical and cost effectiveness of a supraglottic airway device versus tracheal intubation during in-hospital cardiac arrest (AIRWAYS-3)

### 2.2 Aims and objectives

#### 2.2.1 Primary objective

The primary objective of this trial is to determine the clinical and cost effectiveness of SGA versus TI during IHCA by the modified Rankin Scale score assessed at hospital discharge (or at 30 days post-randomisation if the participant remains in hospital).

#### 2.2.2 Secondary objective

The secondary objective of the trial is to conduct an internal pilot study to confirm the feasibility of the large-scale multi-centre trial.

#### 2.3 Outcome measures

The primary outcome for the trial is the modified Rankin Scale score (mRS). This is a 7-point scale that is widely used in cardiac arrest research and often dichotomized into 0-3 versus 4-6 categories, with 0-3 score categories approximating the proportion of patients with a 'good' functional outcome and 4-6 score categories approximating the proportion of patients with a 'poor' functional outcome at hospital discharge (20,21). A mRS score of 6 indicates that the patient has died.

Functional status at hospital discharge is an outcome that is important to both patients and clinicians. The use of the mRS score over other assessment tools (e.g. cerebral performance category) is recommended in the cardiac arrest core outcome set (41).

Survival to hospital discharge and health-related quality of life are included in the cardiac arrest core outcome set (41), and are therefore included as a secondary outcome measure in this trial.

#### 2.3.1 Efficacy

Primary: Modified Rankin Scale (mRS) score assessed at hospital discharge (or at 30 days post-randomisation if the participant remains in hospital).

Secondary:

• Initial ventilation success (visible chest rise with end tidal carbon dioxide monitoring consistent with successful ventilation (where measured) immediately after insertion of a supraglottic airway device or tracheal tube;

• Regurgitation during the resuscitation attempt (stomach contents seen in the patient's pharynx, mouth or nose), and whether this occurred before, during or after advanced airway management;

• Aspiration during the resuscitation attempt (stomach contents seen below the vocal cords, inside a correctly placed tracheal tube or the airway channel of a correctly placed supraglottic airway device), and whether this occurred before, during or after advanced airway management;

- Return of spontaneous circulation (ROSC) for at least 20 minutes;
- Intensive Care Unit length of stay;
- Hospital length of stay;
- Survival to hospital discharge, 3 and 6 months;
- Functional outcome (mRS) score at 3 and 6 months;

• Health-related quality of life at discharge or 30 days (whichever occurs sooner), 3 and 6 months.

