# 2.9 Trial treatments / intervention

#### 2.9.1 Trial treatment(s) / intervention

Intervention: A **supraglottic airway device** of the type used routinely in that hospital. During resuscitation the SGA will be placed according to manufacturer's instructions, with end-tidal carbon dioxide monitoring wherever possible, following an initial period of bag-mask ventilation as required. If a functioning SGA has already been placed at the point of randomisation, and the patient is randomised to SGA, this device may be left in situ. Two attempts at SGA placement should be made. An attempt is defined as introducing a SGA past the teeth, and concludes when the SGA is removed from the mouth. If two attempts at SGA placement are unsuccessful treatment will proceed as dictated by the treating clinician (including tracheal intubation if indicated). If successful, the SGA should be used until resuscitation efforts cease or return of spontaneous circulation (ROSC) is achieved for >20 minutes, at which point further management will proceed as dictated by the treating clinician.

Comparator: **Tracheal intubation.** During resuscitation tracheal intubation should occur, with endtidal carbon dioxide monitoring wherever possible, following an initial period of bag-mask ventilation as required. If a functioning SGA has already been placed at the point of randomisation, and the patient is randomised to tracheal intubation, the SGA should be removed, and tracheal intubation attempted. Two attempts at intubation should be made. An attempt is defined as introducing the laryngoscope past the teeth and concludes when the laryngoscope is removed from the mouth, regardless of whether or not a tracheal tube is inserted. If two attempts at tracheal intubation are unsuccessful subsequent treatment will proceed as determined by the treating clinician (including placement of a SGA if indicated). If successful, tracheal intubation should continue until resuscitation efforts cease or ROSC is achieved for >20 minutes, at which point further management will proceed as dictated by the treating clinician.

Both interventions are part of standard clinical care in the treatment of IHCA and there are no known additional risks to the participants above routine care.

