#### 6.2.3.3 Secondary outcome analysis

Outcome	Source of Data	Justification				

Initial ventilation success (visible chest rise and evidence of end tidal carbon dioxide on capnography)	App data entry following IHCA	Primary goal of advanced airway management is to deliver effective ventilation
Regurgitation (stomach contents visible in the mouth or nose) or aspiration (stomach contents visible below the vocal cords or inside a correctly placed tracheal tube or airway channel of a supraglottic airway device)	App data entry following IHCA	Different advanced airway management techniques may be associated with different risks of regurgitation and/or aspiration
Return of spontaneous circulation (ROSC) > 20 minutes	NCAA and/or data collection by research staff at participating sites	Short-term outcome following cardiac arrest
Critical care length of stay (number of days from randomisation	NCAA and/or data collection by research staff at participating sites, HES	Measure of health service use, Required for health economic analysis
Hospital length of stay (number of days from randomisation)	NCAA and/or data collection by research staff at participating sites, HES	Measure of health service use, Required for health economic analysis
Survival to hospital discharge, 3- months and 6-months	NCAA and/or data collection by research staff at participating sites, HES	Included in the cardiac arrest core outcome set
mRS score at 3-months and 6- months	Postal CRF/eCRF/CRF completed by telephone	Included in the cardiac arrest core outcome set; patient-centred outcome
Health-related quality of life (EQ- 5D-5L) at 3-months and 6-months	Postal CRF/eCRF/CRF completed by telephone	Included in the cardiac arrest core outcome set; required for health economic analysis; patient- centred outcome
In-hospital stay utilization and costs	HES	Required for health economic analysis
Additional unscheduled care and readmission (to 6 months)	HES	Required for health economic analysis
Adverse events/ serious adverse events	CRF (in-hospital patient notes)	All serious adverse events and adverse events that are related to the intervention will be reported, in line with Warwick CTU operating procedures.

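### Counting stomach contents seen in the pharynx as regurgitation gives the TI arm more opportunity to detect it than the SGA arm; the protocol's other definition leaves the pharynx out

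*Protocol*

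**What the plan says.** Section 2.3.1 lists regurgitation among the secondary efficacy outcomes. It is met by "stomach contents seen in the patient's pharynx, mouth or nose", and the record also states its timing: "and whether this occurred before, during or after advanced airway management". The table in section 6.2.3.3 words the outcome differently: "Regurgitation (stomach contents visible in the mouth or nose". The pharynx is not mentioned there. The same table gives the data source as app entry after the arrest, and the reason for the outcome as "Different advanced airway management techniques may be associated with different risks of regurgitation and/or aspiration", so a comparison between arms is intended.

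Section 2.9.1 defines what counts as an attempt in each arm. For TI: "An attempt is defined as introducing the laryngoscope past the teeth and concludes when the laryngoscope is removed from the mouth". For SGA: "An attempt is defined as introducing a SGA past the teeth, and concludes when the SGA is removed from the mouth". In the SGA arm intubation appears only as later management: "If two attempts at SGA placement are unsuccessful treatment will proceed as dictated by the treating clinician (including tracheal intubation if indicated". A working SGA already in place at randomisation may stay in the SGA arm, but is to be taken out before intubation in the TI arm.

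Section 2.10.1 discusses whether knowing the allocation could influence outcomes. It does not discuss whether the two arms have the same chance of revealing an event. Nothing in the protocol asks for equal inspection of the pharynx or for a record of how contents were seen.

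**The concern.** The outcome depends on something being seen, and one qualifying site is seen far more readily with an instrument that only one arm uses by design. Suppose stomach contents lie in the pharynx but have not reached the mouth or nose. A TI operator looking along the laryngoscope may well see them; an SGA operator passing the device may not. Two patients with the same event would then be recorded differently because of their allocation.

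This is unequal opportunity to observe, so it would affect a perfectly honest recorder. Intention to treat, covariate adjustment and a larger sample all leave it in place. It also cannot be repaired at the analysis stage: data are entered once, after the event, and if the app does not mark how the contents were seen, those events cannot later be separated. What is at stake is the interpretation of a prespecified secondary comparison, where the bias would run towards the trial's own hypothesis that SGA is superior.

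**Working it through.** **The protocol's own figure, for background.** Section 6.1 gives 2,095 per group (4,190 in total) for 8.5% v 11.5%, two-sided 5%, 90% power. The unpooled formula gives (1.960 + 1.282)² × (0.085 × 0.915 + 0.115 × 0.885) / 0.03² = 2,097 per group, or 4,194; the pooled formula gives 2,100 per group, or 4,200. The figure reproduces, and this point does not dispute it. Only n = 2,095 per arm is carried forward.

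**Assumptions (none is in the protocol).**
- r: true regurgitation rate, equal in both arms, 10% to 30%.
- s: share of events visible only in the pharynx, 10% to 50%.
- V: probability that such an event is seen in a given arm. Three settings are used: 1 (TI) v 0 (SGA); 0.85 v 0.15, allowing for non-adherence and crossover; and 1 v a value between 0.5 and 0.75, allowing SGA operators to see many of them anyway.

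**Formulas.** Observed rate in an arm = r × [(1 − s) + s × V]. Then z = (TI rate − SGA rate) / √{[p₁(1 − p₁) + p₂(1 − p₂)] / 2,095}, and the chance of a significant result favouring SGA is Φ(z − 1.96). With no bias this chance is 2.5% (5% for both directions). The simple two-proportion test stands in for the planned mixed-effects logistic model.

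**One case in full.** r = 20%, s = 10%, V = 1 v 0: observed 20% v 18%; standard error = √[(0.1600 + 0.1476) / 2,095] = 0.0121; z = 0.02 / 0.0121 = 1.65; Φ(−0.31) = 38%.

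| r | s | V, TI / SGA | Observed, TI v SGA | Odds ratio | Chance of false significance favouring SGA |
|---|---|---|---|---|---|
| 10% | 10% | 1 / 0.75 | 10.0% v 9.75% | 0.97 | 4.6% |
| 10% | 10% | 0.85 / 0.15 | 9.85% v 9.15% | 0.92 | 12% |
| 10% | 25% | 1 / 0.5 | 10.0% v 8.75% | 0.86 | 28% |
| 20% | 10% | 0.85 / 0.15 | 19.7% v 18.3% | 0.91 | 21% |
| 20% | 10% | 1 / 0 | 20.0% v 18.0% | 0.88 | 38% |
| 20% | 25% | 1 / 0.5 | 20.0% v 17.5% | 0.85 | 55% |
| 20% | 20% | 0.85 / 0.15 | 19.4% v 16.6% | 0.83 | 66% |
| 20% | 20% | 1 / 0 | 20.0% v 16.0% | 0.76 | 92% |
| 30% | 25% | 1 / 0.5 | 30.0% v 26.25% | 0.83 | 77% |
| 30% | 50% | 1 / 0 | 30.0% v 15.0% | 0.41 | >99% |

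In the mildest row the other direction adds Φ(−0.27 − 1.96) = 1.3%, for 5.8% in all: practically the nominal rate. Over the whole grid the spurious difference runs from 0.25 to 15 percentage points, and in this model it always favours SGA.

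**Under the section 6.2.3.3 wording**, pharynx-only events are not counted, so s = 0 and this particular difference disappears.

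**The case against.** Several objections have force.

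- **Only one of two definitions has the problem.** The section 6.2.3.3 wording already leaves out the pharynx. This is true, and it is why the remedy is to settle the conflict in that direction. But section 2.3.1 is where the outcomes are defined, and reconciling the other way would fix the asymmetry in place.
- **The attempt definitions are rules for counting attempts.** They do not say what clinicians look at, and pharyngeal contents may be seen without a laryngoscope, for example during suction. Some SGA patients are intubated later, and some TI patients regain circulation before any attempt. All of this dilutes the asymmetry; none of it equalises the arms.
- **The pharynx-only share has no documentary basis.** This stands in full. A reader might infer that even modest under-detection would produce a significant advantage for SGA. The table does not support that: in the milder rows significance is unlikely, and in the mildest the error rate is close to nominal.
- **The direction is not certain for every version of the outcome.** The trial summary and section 6.2.3.3 list regurgitation and aspiration together, and aspiration can be met by contents in the SGA's airway channel, a route specific to that device. For a combined item the net direction cannot be determined. For regurgitation alone, as in section 2.3.1, it runs towards SGA.
- **Importance.** A reader might take this as the trial's main airway-safety comparison. The protocol does not say so: regurgitation is one of several secondary efficacy outcomes, and section 2.3.2 defines safety through adverse events.

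**Conclusion.** The point holds as a should-fix on one secondary outcome. The protocol gives two definitions of regurgitation that differ on exactly the site that one arm is equipped to inspect. Under the section 2.3.1 definition, detection is unequal by design and the comparison can be biased in favour of SGA. That much follows from sections 2.3.1, 2.9.1 and 6.2.3.3 together.

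The size does not follow from the documents. With equal true rates of 10% to 30% and 2,095 per arm, the false-positive rate runs from about 5% to over 99%, depending on how many events are visible only in the pharynx and how often SGA operators see them. The documents therefore do not support saying that a false SGA advantage will be reported, only that it could be and that the data as collected could not reveal it. The mRS primary outcome and the total of 4,190 are untouched.

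**What to change.** 1. Make sections 2.3.1 and 6.2.3.3 agree. For the between-arm comparison, define regurgitation as stomach contents visible at the mouth or nose without a laryngoscope.
2. Add one item to the app form marking contents seen only in the pharynx or at laryngoscopy.
3. Report those events, and the all-sites definition, descriptively by arm.
4. Show the events recorded as occurring before advanced airway management by arm; they are already collected. A difference between arms would hint at detection bias. This is a rough check only, because the time from randomisation to airway placement can differ by arm and the timing is judged afterwards by an unblinded clinician.

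**Cost.** A change of definition and one tick-box; no extra procedure, staff or patients. The compared endpoint has fewer events. At a rate of 20%, the standard error of the log odds ratio grows by √(0.2 × 0.8 / (0.18 × 0.82)) = 1.04, or 4%, if a tenth of events are pharynx-only, and by √(0.2 × 0.8 / (0.14 × 0.86)) = 1.15, or 15%, if three tenths are. The loss is thus small where the bias is small, and larger only where the bias would be large too. Some inequality may remain, since a TI operator also looks into the mouth when introducing the laryngoscope.
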